**Table 4 - Derivation of measurable paraprotein type at baseline**

Measurable paraprotein at baseline	Criteria
Serum M-Protein	Serum M-protein $\geq$ 0.5 g/dL and urine M-protein <200 mg/24 hours or negative or missing urine M-protein
Urine M-Protein	Serum M-protein <0.5 g/dL or negative serum M-protein and urine M-protein $\geq$ 200 mg/24 hours
Serum and urine M-protein	Serum M-protein $\geq$ 0.5 g/dL and urine M-protein $\geq$ 200 mg/24 hours

***Prior anti-myeloma therapies***

- Prior anti-myeloma treatments

Prior anti-myeloma treatments are collected by regimen in the eCRF. The following variables will be summarized/derived:

- Number of prior regimens,
- Number of prior lines (as defined in Appendix E of the study protocol): a line of therapy consists of  $\geq$ 1 completed cycle of a single agent or a regimen consisting of a combination of several drugs, or a planned sequential therapy of various regimens,
- Main anti-myeloma therapies by class and agent
  - Alkylating agents: cyclophosphamide, melphalan, bendamustine,
  - Proteasome inhibitors: bortezomib, carfilzomib, ixazomib,
  - Immunomodulators: lenalidomide, thalidomide, pomalidomide,

- Monoclonal antibodies: elotuzumab and other anti CD38 agents (daratumumab, MOR202)
- Anthracyclines
- Vinca alkaloids
- Corticosteroids
- HDAC inhibitors

In addition, the refractory status to immunomodulators and/or proteasome inhibitors will be derived. A patient will be considered to be refractory to a drug if any of the following conditions is met:

- Progression date and end date are complete and progression is before drug end date or within ( $\leq$ ) 60 days of drug end date. If only the day is missing for either date or both dates, the 2 dates should be separated by no more than 1 month,
- Best overall response is SD or PD,
- Reason for treatment discontinuation is "Disease progression".
- Intolerance to lenalidomide and/or proteasome inhibitors
  - Derived from patients who discontinued lenalidomide and/or proteasome inhibitor after a minimum of approximately 2 consecutive cycles (49 days corresponding to 2 4-week cycles minus 1 week) for AE.
- Description of last regimen given prior to study entry:
  - Time from completion of last line of treatment to first study treatment administration (months),
  - Main treatments,
  - Best response to last regimen,
  - Duration of last regimen of therapy,
  - Refractory status as defined above.
- Prior transplant: number (%) of patients with transplant, type of transplant (autologous, allogenic), number of transplant by patient.
- Prior surgery: number (%) of patients with any prior surgery related to MM, type of procedure and time from last surgery to first study treatment administration (months).
- Prior radiotherapy: number (%) of patients with any prior radiotherapy related to MM, intent and time from last radiotherapy to first study treatment administration (months).

### **2.1.2 Prior or concomitant medications (other than anticancer therapies)**

All medications taken within 21 days before randomization and until the end of the study are to be reported in the case report form pages.

All medications will be coded using the World Health Organization-Drug Dictionary (WHO-DD) using the version MAR2018 or higher.

- Prior medications are those the patient used prior to first investigational medicinal product (IMP) intake. Prior medications can be discontinued before first administration or can be ongoing during treatment phase.
- Concomitant medications are any treatments received by the patient concomitantly to the IMP(s), from first administration to the last dose + 30 days. A given medication can be classified both as a prior medication and as a concomitant medication. Any anti-cancer treatment administered after the date of the last study treatment administration will not be considered as a concomitant medication and will be regarded as a further anti-myeloma therapy (see [Section 2.1.9](#)). The analysis of concomitant medications will include the IR medications (see below).
- Post treatment medications are those the patient took in the period running from 30 days after the last dose up to the end of the study.

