### **Determination of the PFS status for the primary analysis**

The following rules will be applied to determine if a patient has an event or is censored for the PFS primary analysis:

- For a patient who did not die and did not reach progressive disease before the cut-off date, the patient is censored and the censoring date is determined as follows:
  - If the patient received any further anti-myeloma treatment, then the censoring date is the date of last valid disease assessment without evidence of PD before the start of further anti-myeloma treatment, or the cut-off date, whichever comes first,
  - If the patient did not take any further anti-myeloma treatment then the censoring date is the date of last valid disease assessment without evidence of PD or the cut-off date, whichever comes first.
- For a patient who died or reached progressive disease before the cut-off date:
  - If the patient received any further anti-myeloma treatment before death or progression is documented, then the censoring date is the date of last valid disease assessment without evidence of PD before the start of further anti-myeloma treatment,
  - If the patient reached the PFS endpoint before initiation of further anti-myeloma treatment, the date of the event will be the date of progressive disease or death if no progression occurred.

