### **2.1.9 Further therapy after discontinuation of investigational medicinal product administration during the study**

Further therapies after discontinuation of IMP include further anti-myeloma treatments.

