**Sensitivity analysis #4 (PFS considering initiation of further anti-myeloma treatment as an event)**

PFS endpoint will be analyzed based on IRC disease assessments, including initiation of further anti-myeloma treatment as an event. If further anti-myeloma treatment is initiated in absence of documented disease progression per IMWG criteria, the start date of the further anti-myeloma treatment will be used as the date of PFS event. If both initiation of further anti-myeloma treatment and documented disease progression per IMWG criteria are reported, the date of event will be the earliest of the date of documented progression and the start date of further anti-myeloma treatment.

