### ***Second primary malignancies***

A listing of patients who reported second primary malignancies during the study will be provided (as per the CMQ). This listing will include diagnosis, study day of diagnosis (from first dose), number of days from last study treatment to diagnosis, prior exposure to anti-myeloma treatments, and whether or not patient received subsequent anti-cancer treatment.

In addition, treatment-emergent and post-treatment AEs in the CMQ 'Second primary malignancies' will be presented by sub-category ('haematological', 'non-hematological skin tumors', 'non-hematological non-skin tumors' and 'other tumors') and by decreasing incidence of PT.

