## Appendix E Description of primary and sensitivity analyses of PFS

**Table 13 – PFS Primary analysis (based on blinded IRC)**

Situation	Date of progression or censoring	Outcome
No baseline tumor assessments	Date of Randomization	Censored
No valid post-baseline tumor assessments	Date of Randomization	Censored
Documented Progression according to IRC prior to initiation of further anti-myeloma treatment and prior to the cut-off date	Earliest date among all disease assessments with evidence of progression	Event
Death without documented progression prior to initiation of further anti-myeloma treatment and prior to the cut-off date	Date of death	Event
Both documented progression and death prior to initiation of further anti-myeloma treatment and prior to the cut-off date	Date of progression	Event
No documented progression according to IRC and no death prior to initiation of further anti-myeloma treatment and prior to the cut-off date	Earliest of the date of last valid disease assessment without evidence of progression before initiation of further anti-myeloma treatment and cut-off date	Censored
Symptomatic deterioration reported and no documented progression according to IRC and no death	Ignored	Ignored
Initiation of new anti-myeloma treatment before documented progression according to IRC	Earliest of the date of last valid disease assessment without evidence of progression before the initiation of further anti-myeloma treatment and cut-off date	Censored

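### SAP 2.1.2, read literally, turns treatment of a second cancer after the last study dose into further anti-myeloma therapy, which drives TNT, PFS2 and, before progression, PFS censoring

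*SAP*

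**What the plan says.** SAP 2.1.2 defines concomitant medications and then sets a rule for cancer drugs: "Any anti-cancer treatment administered after the date of the last study treatment administration will not be considered as a concomitant medication". The sentence goes on to move such treatment to another category, so that it "will not be considered as a concomitant medication and will be regarded as a further anti-myeloma therapy", with a cross-reference to SAP 2.1.9. That section says only that "Further therapies after discontinuation of IMP include further anti-myeloma treatments". It neither requires a myeloma indication nor excludes treatment of another malignancy.

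The start of further anti-myeloma treatment then drives several efficacy rules:

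- **Primary PFS** (SAP 2.1.3.1, PFS status): "If the patient received any further anti-myeloma treatment before death or progression is documented, then the censoring date is" the last valid assessment before that treatment. Appendix E, Table 13 repeats this: "Initiation of new anti-myeloma treatment before documented progression according to IRC" has the outcome censored.
- **Sensitivity analysis #4**: where no progression is documented, "the start date of the further anti-myeloma treatment will be used as the date of PFS event".
- **TNT** (SAP 2.1.9): the start of such treatment is the event.
- **PFS2** (SAP 2.1.3.2.3, Appendix H): progression is counted only after such treatment has started.
- **PFS on first line of further therapy, and response on subsequent therapy** (SAP 2.1.3.2.3, 2.4.4.3): both are built on these lines of treatment.

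Protocol 11.4.2.1 ties PFS censoring to further treatment for myeloma and does not mention other cancers. The plan does expect other cancers. Second primary malignancy is an adverse event of special interest, and the listing in SAP 2.4.5.1 records previous myeloma treatments and, as a separate item, "whether or not patient received subsequent anti-cancer treatment".

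**The concern.** Treatment for breast or colon cancer says nothing about whether the myeloma has progressed or been re-treated. Under the literal sentence it nevertheless acts as if the patient had moved to a new myeloma regimen.

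The patients exposed are those who stop all study drugs without progression. The protocol follows them monthly until progression is confirmed, so their progressions are observed. The literal rule would then discard a valid IRC progression, or a death, from the primary endpoint. It would also record a new myeloma treatment that was never given.

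The SAP sentence is wider than the protocol's censoring trigger, and neither SAP 1.5 nor Table 1 in SAP 1.6 lists that as a change.

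**Working it through.** **1. The rule traced through one patient.** A hypothetical patient stops all study drugs for an adverse event without progression. Drug treatment for a second cancer starts at Month 6. Progression, by both IRC and investigator, comes at Month 9. All dates fall before the relevant cut-off.

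| Analysis | SAP 2.1.2 read literally | Trigger limited to myeloma treatment |
|---|---|---|
| Primary PFS | Censored at last valid assessment before Month 6 | Event at Month 9 |
| Sensitivity #1 (ignores further treatment) | Event at Month 9 | Event at Month 9 |
| Sensitivity #4 | Event at Month 6 | Event at Month 9 |
| TTP | Censored before Month 6 | Event at Month 9 |
| BOR window | Closes at Month 6 | Stays open to Month 9 |
| TNT | Event at Month 6 | Event only when myeloma treatment starts |
| PFS2 | Event at Month 9, which is really the first progression | Still running at Month 9 |
| PFS on first line of further therapy | 9 − 6 = 3 months, event | Not included until myeloma treatment starts |

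DOR would follow PFS if the patient had responded, because the Clinical Trial Summary applies the same censoring rules to it. Sensitivity analyses #2, #3 and #5 also censor at new treatment, so they share the problem.

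**2. Conditions.** The sentence covers only treatment given after the last study treatment. A second-cancer drug started while any study drug continues is outside it. For PFS and sensitivity analysis #4, the treatment must also start before IRC progression or death. TNT and the further-line summaries do not need that last condition. A second-cancer treatment started after progression but before the next myeloma regimen still gives an early TNT event.

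**3. Missing dates.** SAP 2.5.3 sets a wholly missing start date to the day after treatment end. A misclassified drug with no date would therefore act almost at once.

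**4. Size.** The PFS design figures come from SAP 1.3 and 2.4.4.1: HR 0.60, one-sided 0.025, 90% power, 1:1 allocation, 162 events, critical HR 0.734. They reproduce.

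- Events: 4 × (1.960 + 1.282)² / (ln 0.60)² = 4 × 10.507 / 0.2609 ≈ 161.1, rounded up to **162**.
- Power at 162 events: Φ(0.5108 × √162 / 2 − 1.960) = Φ(1.291) = **90.2%**.
- Critical HR: exp(−2 × 1.960 / √162) = **0.735**, against 0.734 stated.

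The documents give no rate of treated second cancers before progression. As an assumption only, suppose 1%, 2% or 5% of 300 patients lost a PFS event in this way at a fixed cut-off:

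| Events lost | Events left | Power |
|---|---|---|
| 3 (1%) | 159 | 89.6% |
| 6 (2%) | 156 | 89.1% |
| 15 (5%) | 147 | 87.2% |

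The PFS cut-off is set by the 162nd event, so a lost event mainly delays the cut-off. The issue is wrong classification, not power.

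**The case against.** The best reply is that this is housekeeping. The sentence sits in a section whose heading excludes anticancer therapies, and its evident purpose is to keep post-study cancer drugs out of the concomitant medication tables. The endpoint rules all speak of anti-myeloma treatment. The documents also use anti-cancer loosely where they probably mean myeloma therapy, for example in the OS switching analysis (SAP 2.4.4.2) and the patient-reported outcome rules (Protocol 11.4.6). Further anti-myeloma therapy is its own item in the Study Flow Chart, so a second-cancer drug may never reach the field that feeds these rules.

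That makes a narrower intent plausible, and practice may already be right. It does not change the text. The sentence assigns these drugs to the category that the efficacy rules use, and nothing in the SAP makes the eCRF page the sole source.

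Three further points stand and limit the concern:

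- The window for PFS is narrow. The assumed medians are 4 and 6.67 months, the PFS cut-off is about 18 months after first patient in, and exclusion criterion E 20 removes most malignancies within the previous 3 years.
- Sensitivity analysis #1 counts every IRC progression and death whatever treatment follows.
- SAP version 3 postdates the primary PFS analysis, and IRC-based PFS and ORR are not updated later. A new wording cannot prespecify them.

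A purely indication-based rule also has a weakness. SAP 2.1.1 lists cyclophosphamide, anthracyclines, vinca alkaloids and corticosteroids among the main anti-myeloma therapies. Given for another cancer, such drugs could affect M-protein.

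**Conclusion.** The point holds as a defect in a stated rule. Followed as written, SAP 2.1.2 misclassifies treatment of a second cancer. TNT, PFS2 and the further-line analyses would be wrong for any such patient who has stopped all study drugs. Primary PFS and sensitivity analysis #4 would be wrong only if the treatment also precedes IRC progression or death. The expected number of patients is small, no rate can be drawn from the documents, and the power figures above rest on assumed percentages.

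A reader might infer more, and the documents do not support it:

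- **That the primary PFS result was distorted.** Nothing shows that any patient met the conditions, or that the programming followed the literal sentence.
- **That one arm is favoured.** The documents give no second-cancer rates by arm.
- **That a particular number of patients is affected.** Any such count would rest on an invented rate and an invented progression-free share.

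A correction is worth making because the main remaining exposure lies ahead. TNT, PFS2 and the further-therapy analyses are scheduled for the second interim and final OS analyses, at about 43 and 51 months.

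**What to change.** 1. In SAP 2.1.2, limit the sentence to anti-cancer treatment given for multiple myeloma. Identify it by the recorded indication or by the further anti-myeloma therapy eCRF page, and repeat the definition in SAP 2.1.9.
2. State that treatment for another malignancy follows the ordinary timing rules of SAP 2.1.2: concomitant up to 30 days after the last dose, post-treatment after that. It triggers no rule for PFS, TTP, DOR, BOR, TNT or PFS2. Calling it post-treatment from the day of the last dose would contradict the 30-day window. Because the section heading excludes anticancer therapies, note the exception there.
3. Flag any such patient whose second-cancer treatment uses a drug class listed as anti-myeloma in SAP 2.1.1. A listing is enough, read beside sensitivity analysis #1, which counts their progressions and deaths in any case.
4. Apply the definition to TNT, PFS2, PFS on first line of further therapy and the subsequent-line summaries at the second interim and final OS analyses.
5. For the completed primary PFS analysis, state how many such patients there were, if any, and how they were handled. If there were none, one line in the study report closes the point.

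The cost is a short SAP clarification, an indication check in the programming, and a look through the second primary malignancy listing. No new data are needed if the indication or source page is already recorded.

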## **IR medications**

As defined in Section 8.2.2 of the study protocol, patients will routinely receive premedications prior to isatuximab infusion to reduce the risk and severity of infusion reactions (IRs) commonly observed with monoclonal antibodies. Premedications are defined in the protocol as non-investigational medicinal product(s) and should be reported in a specific form of the eCRF. Analysis of premedications will focus on those given (drug class, start and stop dates) for prophylaxis reason. Dexamethasone being part of study treatment and reported in IMP form of the CRF, only steroids reported in the IR medication eCRF form will be described with IR medication.

Medication given in curative intent of IR will be also analyzed by type (Diphenhydramine or equivalent, steroids, paracetamol or equivalent).

Any technical details related to computation, dates, imputation for missing dates are described in [Section 2.5](#).

### **2.1.3 Efficacy endpoints**

#### **2.1.3.1 Primary efficacy endpoint(s)**

The primary endpoint is Progression Free Survival (PFS) defined as the time from the date of randomization to the first documented date of progressive disease or death due to any cause before the analysis cut-off, whichever comes first. Patients without disease progression or death before the analysis cut-off or the date of initiation of further anti-myeloma treatment, will be censored at the earliest of the date of the last valid disease assessment not showing disease progression performed prior to initiation of a further anti-myeloma treatment (if any) or the analysis cut-off date, whichever comes first.

An independent response committee (IRC) blinded to the randomization arm and to the patient characteristics will evaluate disease assessments at each time point and determine disease response including progression status per IMWG criteria (1) ([Appendix D](#)). The full details regarding the determination of the progressive disease are provided in protocol and the IRC charter. The date of disease progression as determined by the IRC will be used for primary PFS analysis.

A patient without PFS event (death or disease progression) and without any valid post-baseline disease assessments will be censored at the day of randomization (Day 1).

Additional details regarding the definition of PFS and handling of events and censoring are given in [Appendix E](#).

Other censoring rules used for sensitivity analyses are provided in [Section 2.4.4.1.1](#).

### **Assessment of progression**

Efficacy assessment will be performed on Day 1 of every cycle during treatment. After treatment discontinuation, for patients who discontinued study treatment for reasons other than progression, disease assessments will be performed every 4 weeks during follow-up until PD.

Response and progression as per IRC will be determined on the basis of central laboratory findings, bone marrow biopsy/aspiration if any, and evaluation of plasmacytomas/bone lesions if any, according to IMWG criteria ([Appendix D](#)). Progression based on paraprotein will have to be confirmed based on 2 consecutive assessments. An assessment performed after the initiation of a further anti-myeloma treatment will be used to confirm progressive disease. In addition, death due to progressive disease occurring within 45 days of the first documentation of progression (regardless initiation of further therapies) will be used to confirm PD.

Progression based on plasmacytomas/bone lesions does not require confirmation.

Symptomatic deterioration will not be considered progression in the primary analysis of PFS.

Progression cannot be diagnosed on free light chain (FLC) progression only. For patients with non-measurable M-Protein on Cycle 1 Day 1, PD can be diagnosed on the following parameters:

- For patients with only FLC measurable: M-protein, plasmacytomas, according to IMWG criteria described above
- For patients with non-measurable disease: M-protein, plasmacytoma, according to IMWG criteria described above

### **Date of disease progression determination**

The date of the disease progression is the earliest date that indicates disease progression (provided that the progression is subsequently confirmed in case of progression requiring confirmation). Details will be provided in the Independent Review Charter.

### **Determination of the PFS status for the primary analysis**

The following rules will be applied to determine if a patient has an event or is censored for the PFS primary analysis:

- For a patient who did not die and did not reach progressive disease before the cut-off date, the patient is censored and the censoring date is determined as follows:
  - If the patient received any further anti-myeloma treatment, then the censoring date is the date of last valid disease assessment without evidence of PD before the start of further anti-myeloma treatment, or the cut-off date, whichever comes first,
  - If the patient did not take any further anti-myeloma treatment then the censoring date is the date of last valid disease assessment without evidence of PD or the cut-off date, whichever comes first.
- For a patient who died or reached progressive disease before the cut-off date:
  - If the patient received any further anti-myeloma treatment before death or progression is documented, then the censoring date is the date of last valid disease assessment without evidence of PD before the start of further anti-myeloma treatment,
  - If the patient reached the PFS endpoint before initiation of further anti-myeloma treatment, the date of the event will be the date of progressive disease or death if no progression occurred.

